## 4.2.2 **Protocol Deviations**

## 4.2.2.1 Definitions and Derivations

Important protocol deviations (IPDs) are defined as protocol deviations that may significantly affect the completeness, accuracy, and/or reliability of the study data or that may significantly affect a subject's rights, safety, or well-being. IPDs are defined in detail in the Protocol Deviation Specification Document., but will generally include, but are not limited to:

- Key Inclusion criteria
- Key Exclusion criteria
- Discontinuation criteria for study product met but subject not withdrawn from study treatment
- Investigational Product (IP) Deviation
  - Subjects deviating from the prescribed dosing regimen.
  - Dose modifications (not related due to either an immune or a non-immunerelated AE according to Dosing Modification and Toxicity Management Guidelines)
- Excluded medication taken
  - Received prohibited concomitant medications or therapies (including other anticancer agents).
- Deviations related to study procedure
  - Baseline Response Evaluation Criteria in Solid Tumours (RECIST) version 1.1 scan > 28 days before randomisation..
  - $\circ$  No baseline RECIST 1.1 assessment on or before date of randomisation.

- Other important protocol deviations
  - Deviation from Good Clinical Practice (GCP) as determined by medical review

If a deviation is serious enough to have a potential impact on the primary analysis, sensitivity analyses may be performed. A list of IPDs according to the Protocol Deviation Specification Document is compiled and new potential IPDs are classified by the global lead physician and an unblinded biostatistician trailed by AZ study physician and AZ clinical operations review approximately every 4-5 weeks. The Protocol Deviation Specification Document and the final IPD list will be finalised prior to database lock. Presentation

The incidence of important protocol deviations (IPDs) are summarised for the full analysis set.

- Number of subjects with at least 1 important protocol deviation further split by reason related to;
- Number of subjects with at least 1 pandemic related important protocol deviation further split by reason related to;
- Number of subjects with at least 1 important protocol deviation, excluding pandemic related IPDs further split by reason related to.

A listing is provided with the important protocol deviation details.

#### 4.2.3 Demographics

#### 4.2.3.1 Definitions and Derivations

Age group is defined as a categorical variable with levels  $<18, \ge 18, <50, \ge 50, <65, \ge 65, <75$  and  $\ge 75$  years. Each race category counts subjects who selected only that category.

#### 4.2.3.2 Presentation

Demographics are summarised and listed based on the FAS by treatment arm and for all subjects combined as defined by the current relevant TFL standards. The following are summarised: age (years) at baseline, age group, sex, race and ethnicity. Additionally, the number and percentage of subjects recruited in each country and each centre are presented.

#### 4.2.4 **Baseline Characteristics**

#### 4.2.4.1 Definitions and Derivations

Body Mass Index is calculated as weight/height (kg/m^2).

#### 4.2.4.2 Presentation

Baseline characteristics are listed and summarised according to Section 3.2 for the FAS by treatment arm and for all subjects combined as defined by the current relevant TFL

standards. The following are summarised: weight (kg), height (cm), body mass index  $(kg/m^2)$ .

## 4.2.5 Disease Characteristics

#### 4.2.5.1 **Definitions and Derivations**

Not applicable.

#### 4.2.5.2 Presentation

Disease characteristics at baseline are listed and summarised in terms of absolute counts and percentages affected of subjects for the FASby treatment arm and for all subjects combined as defined by the current relevant TFL standards.

The following are summarised:

- Extend of disease at study entry (metastatic, locally advanced disease, both metastatic and locally advanced, location)
- Disease characteristics at baseline (Eastern Cooperative Oncology Group [ECOG] performance status, primary tumour location, primary tumour type, number of metastases, histology type, primary tumour stage, regional lymph nodes stage, distant metastases stage, tumour grade, Stage/AJCC stage, resistance to prior IO treatment [IVRS], and baseline LDH level [IVRS])
- Mutation status at study entry (Proto-oncogene c-KIT [KIT], neurofibromatosis type 1 [NF1], ataxia telangiectasia and Rad3-related protein [ATR], ataxia telangiectasia mutated [ATM], AT-rich interactive domain-containing protein 1A [ARID1A], B-Rapidly Accelerated Fibrosarcoma gene [BRAF] V600 Mutation and subtype, NRAS proto-oncogene, GTPase [NRAS] Activating Mutations and microsatellite instability [MSI]-High Genetic or Immunohistochemistry)

Recurrence of earlier cancer is depicted in a listing.

#### 4.2.6 Medical History and Concomitant Disease

#### 4.2.6.1 **Definitions and Derivations**

Medical and surgical history is coded using Medical Dictionary for Regulatory Activities (MedDRA).

#### 4.2.6.2 Presentation

Medical history and concomitant disease are listed and summarised for the FAS by treatment arm and for all subjects combined as defined by the current relevant TFL standards.

A separate summary of medical history for subjects who had confirmed or suspected COVID-19 infection during the study is presented. If less than five events appear and less than 2% of randomized subjects are affected the summary will not be visualised.

Additionally, the following is summarised in terms of numbers and percentage of subjects who had:

- Previous disease related treatment modalities (cytotoxic chemotherapy, targeted therapy, antiangiogenic therapy, taxane chemotherapy, radiopharmaceuticals, platinum chemotherapy, experimental therapy, transarterial chemoembolization [TACE], transarterial radioembolization [TARE], immunotherapy, other, number of previous chemo regimens, number of prior lines of systemic therapy, reason for therapy failure of previous cancer therapy, and treatment status of previous cancer therapy)
- Previous Anti-PDL1 therapies (Therapy class, treatment status, Reason for Therapy discontinuation, type of resistance of prior Anti-PDL1, name of prior Anti-PDL1 agent)

Summaries for the number and percentage of subjects wo had a certain number of prior regimens and response assessment results are produced.

The number and percentage of subjects who had prior cancer therapies are summarised by ATC classification and generic drug name.

Results from the Hepatitis B and C and HIV tests at screening are depicted in a listing.

## 4.2.7 Prior and Concomitant Medications

## 4.2.7.1 Definitions and Derivations

For the purpose of inclusion in prior and/or concomitant mediation or therapy summaries, incomplete medication or radiotherapy start and stop dates are imputed as detailed in Section 3.2.8.

Prior medications, concomitant are defined based on imputed start and stop dates as follows:

- Prior medications are those taken prior to study treatment with a stop date prior to the first dose of study treatment.
- Concomitant medications are those with a stop date on or after the first dose date of study treatment, and must have started prior to or during treatment so there is at least one day in common with the study treatment.

#### 4.2.7.2 Presentation

The following summaries are provided in terms of absolute counts and percentages affected of subjects for the FAS o by treatment arm and for all subjects combined as defined by the current relevant TFL standards using ATC classification code and the generic term coded by standard drug dictionary WHODrug Global B3 Mar 2022 or later:

- summary of prior medications or therapies
- summary of concomitant medications or therapies

Additionally, the following is summarised in terms of numbers and percentage of subjects who had:

• Previous Anti-PDL1 therapies (Therapy class, treatment status, Reason for Therapy discontinuation, type of resistance of prior Anti-PDL1, name of prior Anti-PDL1 agent)

Also, all important recorded information for previous Anti-PDL1 therapies will be visualised in a listing.

## 4.3 Endpoint Analyses

This section covers details related to the endpoint analyses such as primary, secondary, other endpoints including sensitivity and supportive analyses.

Efficacy analyses, except for OS, are based on BICR assessments. All images are collected centrally whether scheduled or unscheduled. The imaging scans are reviewed by 2 independent radiologists using RECIST 1.1 and are adjudicated, if required. For each postbaseline visit scan, the BICR defines the overall visit response data (complete response [CR], partial response [PR], stable disease [SD], progressive disease [PD], or not evaluable [NE] depending on the status of their disease compared with baseline and previous scans by assessing TLs, non-target lesions (NTLs) and new lesions) and the relevant scan dates for each time point (i.e., for visits where response or progression is/is not identified). Subjects who have disease progression on study treatment based on progression of non-target disease, may also require submission of additional scans/images/photographs e.g., brain scan or photographs of cutaneous lesions. If a subject has had a tumour assessment that cannot be evaluated, then the subject is assigned a visit response of not evaluable (NE) (unless there is evidence of progression, in which case the response is assigned as PD). No programmatic derivation of visit response is necessary. The date of progression is provided (by each reviewer) based on the earliest of the scan dates of the component that triggered the progression. Endpoints ORR, DoR, BOR, TTR, DCR, and PFS are then derived from the scan dates and overall visit responses. Confirmation of progression is not required.

Details on the adjudication process can be found in the CSP section 8.1.1.2.

As per the sensitivity analyses, efficacy analysis, except for OS, are also based on programmatic application of RECIST 1.1. (Eisenhauer et al, 2009) to investigator assessed tumour measurements. All RECIST 1.1 assessments, whether scheduled or unscheduled, are included in the calculations. This is also regardless of whether a subject discontinues study treatment or receives another anti cancer therapy. At each visit, subjects are
programmatically assigned a RECIST 1.1 visit response of CR, PR, SD, PD, or NE depending on the status of their disease compared with baseline and previous assessments.

Baseline should be assessed within the 21 days prior to randomisation. The tumour response endpoints (ORR, DoR, BOR, TTR, PFS, and change in TL tumour size) are then derived from the scan dates and overall visit responses. Programmatic derivation guidance used for the application of RECIST 1.1 are provided in Section 3.2.10 which is to determine disease response.

Another sensitivity analysis for ORR based on the dosed subjects who have measurable disease at baseline by BICR (response evaluable set) may be conducted.

RECIST data, overall visit response and best objective response are listed.

All efficacy analyses are presented by treatment group.

# **Subgroup Analyses**

The purpose of the subgroup analyses is to assess the consistency of treatment effect across expected prognostic and/or predictive factors.

The subgroup analyses described below are applicable for the primary endpoint (ORR) and for selected secondary endpoints (DoR, PFS and OS)

Subgroups analyses are conducted in the following subgroups:

- Resistance to prior IO treatment (primary / early relapse on adjuvant versus acquired)
- Baseline LDH (<= ULN, >ULN but <2x ULN, >= 2x ULN)
- Sex (male versus female)
- Age at randomisation (<65 years versus >= 65 years of age)
- Melanoma subtype (cutaneous versus acral versus mucosal)
- Presence of liver metastases (yes versus no)
- Presence of brain metastases (yes versus no)
- BRAF Mutation Status (Mutation detected versus Mutation not detected/Not done/unknown)
- Targeted Therapy as Previous Cancer Therapy Class (yes versus no)

Other baseline variables may also be assessed if there is clinical justification or an imbalance is observed between the treatment arms.

The subgroup analyses for the stratification factors are based on the values entered into the IWRS; all other factors are based on the values recorded on the eCRF, or from the third-party vendor data.

If there are too few responders available for a meaningful analysis of a particular subgroup comparison (it is not considered appropriate to present analyses where there are less than 10 responders across both treatment groups in a subgroup comparison), the subgroup analysis will not be performed. In this case, only descriptive summaries will be provided. The same process will be applied to the secondary endpoints PFS and OS if there are less than 20 events across both treatment groups in a subgroup comparison.

# 4.3.1 Primary Endpoint: Objective Response Rate

The primary efficacy endpoint is ORR by BICR.

#### 4.3.1.1 Definition

ORR is defined as the proportion of subjects who have a complete response (CR), or partial response (PR), as determined by BICR per RECIST 1.1, prior to any evidence of progression (as defined by RECIST 1.1), that is confirmed at least 4 weeks later. ORR based on BICR is defined as the percentage of subjects with at least two post-baseline BICR-assessed visit response of CR or PR, with the denominator defined as the number of subjects in the Safety analysis set. For the sensitivity analysis, the subset of subjects in the Response evaluable set is used. For the comparative analysis of ORR between treatment arms the FAS is used instead (see Section 4.3.1.6).

The ORR analysis by BICR will be repeated for investigator data.

#### 4.3.1.2 Derivations

A confirmed response of CR/PR means that a response of CR/PR is recorded at 1 visit and confirmed by repeat imaging not less than 4 weeks after the visit when the response was first observed with no evidence of progression between the initial and CR/PR confirmation visit. Data obtained up until progression, or last evaluable assessment in the absence of progression, are included in the assessment of ORR. Also only data obtained before the start of subsequent anticancer treatment (excluding radiotherapy) are included. Therefore both visits contributing to a confirmed response must be prior to progression and prior to subsequent anticancer treatment.

In the case where a subject has two non-consecutive visit responses of PR, then, as long as the time between the 2 visits of PR is greater than 4 weeks and there is no PD between the PR visits, the subject is defined as a responder. Similarly, if a subject has visit responses of CR, NE, CR, then, as long as the time between the 2 visits of CR is greater than 4 weeks, then a best response of CR is assigned.

# 4.3.1.3 Handling of Dropouts and Missing Data

If any of the randomised subjects at the time of the respective analysis (primary, CCI) have no measurable disease at baseline as per BICR, then an additional analysis of ORR will be conducted for the Response evaluable set.

# 4.3.1.4 Primary Analysis of Primary Endpoint

Summaries are produced that present the number and percentage of subjects with a confirmed tumour response (CR/PR). The ORR is presented for each treatment arm non-comparatively with a two-sided 95% CI using the Clopper-Pearson (exact probability) method. Subjects that have missing overall response assessments at all visits are considered as non-responders, and are therefore counted in the denominator of ORR. The main analysis of ORR is based on the Safety analysis set.

# 4.3.1.5 Sensitivity Analyses of the Primary Endpoint

As a sensitivity analysis, ORR is analysed according to Section 4.3.1.4 but using the investigator assessment per RECIST 1.1.

# 4.3.1.6 Secondary measure of interest of the Primary Endpoint: odds ratio of the ORR

ORR is compared between the treatment arms using logistic regression adjusting for PD-(L)1 resistance type and LDH per randomisation stratification as covariates. The results of the analysis are presented in terms of an odds ratio for study treatments together with associated 95% profile likelihood CI and p-value (based on twice the change in loglikelihood resulting from the addition of a treatment factor to the model). This comparative analysis is provided using the full analysis set.

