There is no standard of care after anti-PD-(L)1 immunotherapy for the intended patientpopulation. Objective response rate for chemotherapy treatment options for patient second line and beyond, post-ipilimumab, are previously reported to be 4% (95% CI 2%, 9%) and 10% (95% CI 5%, 16%). There is no prospective clinical trial data on response rates forchemotherapy specifically in the post CPI-resistant setting. An ORR of % is considered an upper limit of expected response rate for alternative available treatment options for theintended patient population in this study. Per the proposed Phase 2 study design, with100 evaluable patients in the ceralasertib and durvalumab combination therapy arm, successwill be achieved if a minimum ORR of % is observed, for which the %% exact CI wouldbe (CCI %, CCI %).

A secondary objective is to compare the ORR between the two treatment arms. With150 patients (100 patients randomized to ceralasertib and durvalumab combination therapyarm and 50 patients randomized to ceralasertib monotherapy), there will be at least % power at a % of % to detect a difference in ORR, assuming an ORR for ceralasertib plus durvalumab of % and an ORR for ceralasertib monotherapy of %.

It is anticipated at least approximately % of all randomized patients will have progressed or died at the time of the primary analysis. However, if this is not the case, a later analysis for PFS may be conducted once approximately % of all randomized patients have progressed or died.

analysis will be conducted once approximately % of all randomized patients have

died, or years from when the last patient starts treatment, whichever is earliest.

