#### **3.2.2** Study Treatment

The main study is a Phase 2, randomised, open-label, multicentre, international study assessing the efficacy and safety of ceralasertib and ceralasertib plus durvalumab in subjects with unresectable or advanced melanoma and primary or secondary resistance to programmed death-ligand 1 [PD-(L)1] inhibition. Approximately 150 subjects are randomised, at a 2:1 randomisation ratio (approximately 100 subjects in Arm 1 and approximately 50 subjects in Arm 2) to the following intervention groups:

- Arm 1: Ceralasertib 240 mg BD oral tablets, from Days 1 to 7 plus durvalumab 1500 mg Day 8, IV infusion, Q28D, until progressive disease, (confirmed RECIST 1.1-defined radiological progression), unacceptable toxicity, withdrawal of consent, or if a study treatment discontinuation criteria is met.
- 2. Arm 2: Ceralasertib 240 mg BD oral tablets, from Days 1 to 7, Q28D, until progressive disease, (confirmed RECIST 1.1-defined radiological progression), unacceptable toxicity, withdrawal of consent, or if a study treatment discontinuation criterion is met.

Crossover within the study is not be permitted. There is no defined maximum treatment duration for the treatment arms as the subjects receive study treatment until progressive disease (RECIST 1.1-defined radiological progression), unacceptable toxicity, withdrawal of consent, or if a study treatment discontinuation criterion is met.

Randomisation into the treatment arms is stratified by:

• Resistance to prior immune-oncology treatment (primary/early relapse in adjuvant setting vs secondary resistance).

• Baseline lactate dehydrogenase (LDH) expression (below and equal to the upper limit of normal vs above upper limit of normal).

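### The between-arm ORR comparison has no provision for few responders: at a low common ORR its p-value is anti-conservative, and with no monotherapy responder its odds ratio does not exist

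*SAP*

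**What the plan says.** Section 4.3.1.6 defines the comparison: "ORR is compared between the treatment arms using logistic regression adjusting for PD-(L)1 resistance type and LDH per randomisation stratification as covariates". The result is an odds ratio with its "associated 95% profile likelihood CI" and a "p-value (based on twice the change in loglikelihood resulting from the addition of a treatment factor to the model"). The population is stated as well: "This comparative analysis is provided using the full analysis set".

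The size comes from section 3.2.2: "Approximately 150 subjects are randomised, at a 2:1 randomisation ratio (approximately 100 subjects in Arm 1 and approximately 50 subjects in Arm 2"). Section 3.2.1 makes the comparison of ORR between arms a secondary objective, but its power, significance level and assumed ORRs are redacted ("there will be at least % power at a % of % to detect a difference in ORR"). The only response rates left visible are 4% and 10%, reported for chemotherapy after ipilimumab.

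The one rule for sparse responders is in section 4.3 under Subgroup Analyses. A subgroup analysis is replaced by descriptive summaries when there are "less than 10 responders across both treatment groups in a subgroup comparison". Section 4.3.1.6 has no such rule for the overall comparison.

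**The concern.** Likelihood-ratio tests and profile intervals rest on large-sample theory, and what counts is the number of responders, not the number of subjects. When responders are few, two things can go wrong.

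First, if the monotherapy arm has no responder, the likelihood keeps rising as the treatment coefficient grows. There is then no finite estimate and no upper confidence limit. The change in log-likelihood still converges, so a p-value would be printed beside an odds ratio that does not exist.

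Second, with few responders the chi-square reference distribution is too lenient, so a nominal 5% test rejects a true null more than 5% of the time.

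At stake is a stated secondary objective. If the plan is silent, the choice of a replacement method would be made after the problem has appeared in the data.

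**Working it through.** **Inputs.** 100 versus 50 subjects (3.2.2), all in the full analysis set. Treatment plus two binary stratification factors, and a likelihood-ratio test on 1 df (4.3.1.6). Assumptions: a two-sided 5% level, to match the 95% interval; ordinary maximum likelihood, because no penalty is named; and the ORRs, because the planning values are redacted. The plan shows no figure for this comparison that could be reproduced.

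**Step 1: empty monotherapy arm.** P(0 of 50) = (1 − p)^50. For example, 0.96^50 = 0.130.

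**Step 2: type I error.** For a responders of 100 and b of 50, the unadjusted statistic is LR = 2[l(a/100) + l(b/50) − l0], where l0 uses the pooled rate (a + b)/150. The null probabilities of all 101 × 51 tables with LR > 3.84 were summed. The adjusted model was then simulated with 40,000 null trials per scenario, three assumed stratum mixes, and covariate log odds ratios of either zero or −0.7 and −0.9. The Firth penalised likelihood-ratio test was simulated with 20,000 trials per scenario.

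| Common ORR | Expected responders (150p) | P(0/50) | LR, exact, unadjusted | LR, adjusted model | Firth, adjusted model |
|---|---|---|---|---|---|
| 2% | 3.0 | 36% | 5.9% | 5.6–6.0% | 1.6% |
| 3% | 4.5 | 22% | 7.5% | 7.4–7.6% | 2.7% |
| 4% | 6.0 | 13% | 8.0% | 7.7–8.2% | 3.3% |
| 5% | 7.5 | 7.7% | 7.4% | 7.4–7.8% | 3.9% |
| 6% | 9.0 | 4.5% | 6.6% | 6.6–7.1% | 3.9% |
| 8% | 12.0 | 1.5% | 5.5% | 5.7–6.2% | 4.1% |
| 10% | 15.0 | 0.5% | 5.5% | 5.8–6.1% | 4.5% |
| 15% | 22.5 | 0.03% | 5.4% | 5.4–5.9% | 4.8% |
| 20% | 30.0 | <0.01% | 5.2% | 5.3–5.5% | not run |

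The two problems are linked. At an ORR of 4% to 5%, 4.3 to 4.8 percentage points of the exact type I error come from tables with no monotherapy responder.

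**Step 3: a worked table.** For 5/100 versus 0/50, unadjusted:
- l0 = 5 ln(5/150) + 145 ln(145/150) = −21.92
- l1 = 5 ln(0.05) + 95 ln(0.95) = −19.85
- LR = 2 × 2.07 = 4.14, p = 0.042

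The same sum for 4/100 versus 0/50 gives LR = 3.30, p = 0.069. Against an empty monotherapy arm, five responders in the combination arm are therefore enough for significance.

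With the covariates in the model:

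| Data | Method | Odds ratio | 95% CI | p |
|---|---|---|---|---|
| 5/100 v 0/50 | Ordinary ML | none finite | 1.10 to no upper limit | 0.042 |
| 5/100 v 0/50 | Firth | 5.73 | 0.64 to about 755 | 0.14 |
| 10/100 v 0/50 | Ordinary ML | none finite | 2.56 to no upper limit | 0.0036 |
| 10/100 v 0/50 | Firth | 11.5 | 1.44 to about 1490 | 0.015 |

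**The case against.** The strongest reply is that few responders is an assumption. That stands. A reader might take the visible 4% and 10% as the rates expected in this trial, but they are historical chemotherapy rates used as outside comparators, and the rates assumed for the two arms are redacted. The inflation is material only when both arms share an ORR of about 3% to 6%, that is, 4.5 to 9 expected responders in 150. Section 5 also lets the IDMC recommend stopping recruitment to an arm for low response. The calculations run every trial to 100 versus 50 and ignore this, because the thresholds are redacted. Stopping monotherapy early would make an empty arm more likely.

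A reader might also infer that the trial would be left without a usable efficacy result. The SAP does not support that. Section 4.3.1.4 reports each arm's ORR with an exact interval, section 3.2.1 ties success to the combination arm's own ORR, and section 3.2.7 plans no multiplicity adjustment. Even with 0/50 the lower profile limit is finite.

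Nor does it follow that subgroup odds ratios will often be undefined. The SAP does not say that the 4.3.1.6 model is used in subgroups, and the 10-responder rule removes most such cases. In an assumed 33 versus 17 subgroup with combination ORR 20%, the chance of both passing the rule and having no monotherapy responder is 7.6% at monotherapy ORR 2% and 4.5% at 5%.

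What remains is that 4.3.1.6 fixes a method that can misstate the evidence over a credible range and gives no fallback. The authors saw the sparse-responder problem in subgroups but did not cover the overall comparison.

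**Conclusion.** The point holds in a limited form. Followed as written, section 4.3.1.6 gives a two-sided type I error of about 6.6% to 8% if the common ORR is about 3% to 6%. At 8% to 10% it is about 5.5% (exact, unadjusted) to 6% (adjusted model), and by 20% it is close to nominal. With no monotherapy responder the plan yields no odds ratio and no upper limit, possibly beside a significant p-value.

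This rests on assumed ORRs, a 5% level, full recruitment to 100 versus 50, and reading the unnamed fitting method as ordinary maximum likelihood. It concerns a secondary comparison and leaves the primary per-arm analysis untouched. It should be corrected before the comparison is run, but it does not threaten the trial's main conclusion.

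**What to change.** In 4.3.1.6, pre-specify Firth penalised logistic regression with the same two stratification covariates. Take the odds ratio, the penalised profile-likelihood 95% CI and the penalised likelihood-ratio p-value all from that one model, so that test and interval agree. At minimum, apply it when there are fewer than 10 responders in total or none in either arm. Use the same method for any ORR subgroup odds ratio where one arm has no responder.

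The cost is SAP wording, a standard software option and a few points of nominal power. By the same exact unadjusted enumeration, Firth throughout lowers power from 84% to 79% at 15% versus 2%, and from 80% to 75% at 20% versus 5%. Part of that reflects the current test exceeding its level. The minimum version costs less than half a point in both cases. Its exact unadjusted type I error is 3.9% at a common ORR of 5%, 5.0% at 8% and 5.4% at 10% to 15%. With an empty arm the Firth interval is finite but very wide, and it should be reported as such.
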